1) Every six months, a questionnaire with a Likert scale (ordinal scale graded from 1 to 5, e.g 1=Strongly Agree, 5=Strongly disagree) and free text (unstructured response) questions will be administered to the PEPFAR staff and peer educators on their impressions of the intervention and suggestions for improvement. 2) Peer educators will be required to demonstrate knowledge and skills with an oral and practical test following bimonthly, one-day continuing education sessions. 3) RHSP field staff will perform spot checks of peer educator home visits during the initial 2 months of implementation. 4) Peer educator home visit forms will be entered into an electronic database and descriptive statistics compiled. This is an ongoing evaluation of personnel for QA/QC purposes.

Population:

Sample Size

The total number of PEPFAR patients expected to be enrolled by May 2007 is \sim 1000, so we anticipate \sim 330 patients in each of the three study arms. We already have \sim 6 months follow up information on \sim 800 patients in the pilot study. With a further one year follow up we will have information over \sim 18 months. Assuming a 5% drop out rate, we anticipate \sim 5,643 person months (\sim 470 py) per study arm. Detectable viral load (i.e., virologic failure) is \sim 28%. ¹²

Power Calculations or Statistical Plan

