This is an unmatched community randomized study. However, the Rakai communities have been selected to be homogeneous, and prior estimates indicate a coefficient of variation (k) between clusters of 0.24. Thus, design effects are modest (\sim 1.26). With a two-sided α = 0.05 and 1-β of 0.80, the study will have the power to detect a reduction in virologic failure in either intervention arm relative to the control arm with rate ratio (RR) \leq 0.70 (i.e., a failure rate ≤ 19.6%). If the two peer educator intervention arms are compared to the control arm, the study will have a power to detect a reduction in virologic failure of RR ≤ 0.74 (i.e. ≤ 20.7%). Descriptive analyses will compare patients in each study arm at time of enrollment with respect to sociodemographic characteristics, WHO stage, viral load, CD4 count and Karnofsky score. Univariate analyses will assess outcomes by strata of covariates in each intervention arm. For dichotomous outcomes (e.g., virologic failure, drug toxicity, OIs, and mortality) we will use multivariate log-binomial regression to estimate the relative risk of treatment failure, adherence etc. between intervention arms, adjusted for covariates found to differ between arms at p < 0.15 in univariate analyses, or suspected confounders. Adjustment for clustered data will use general estimating equations (GGE) to estimate robust variances. For continuous data (e.g., adherence percent, CD4 changes from baseline to follow-up, number of drug toxicity events) we will use tests and analysis of variance (ANOVA). The effects of peer educators and mobile phone interventions will be assessed by stratified analyses and by interaction terms. The number of treatment failures prevented will be estimated.

Inclusion and Exclusion Criteria

Inclusion in the study is determined by receipt of ARVs in the PEPFAR program. This protocol however deals only with the analysis of de-identified data and the intervention received by subjects takes place under a different service program.

Gender, Age and Locale

Both males and females between ages <1 and 60 are included.

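### Deaths, opportunistic infections and drug toxicity are compared as yes/no risks, and toxicity counts by ANOVA, with no allowance for follow-up that appears to run from about 12 to about 18 months

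*Protocol*

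**What the plan says.** Protocol, Power Calculations or Statistical Plan, names the models. On binary outcomes: "For dichotomous outcomes (e.g., virologic failure, drug toxicity, OIs, and mortality) we will use multivariate log-binomial regression", giving relative risks between arms, with robust variances from estimating equations for clustering. Drug toxicity appears a second time, as a count grouped with continuous data: "number of drug toxicity events) we will use tests and analysis of variance (ANOVA"). Adjustment covers covariates that differ between arms at p < 0.15, or suspected confounders. Follow-up time is not named among them. No offset, rate model, survival method or fixed risk window is given for mortality, OIs or toxicity.

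Protocol, Sample Size, expects about 1000 patients, or about "330 patients in each of the three study arms". It reports some 6 months of existing information on about "800 patients in the pilot study", and continues: "With a further one year follow up we will have information over" about 18 months. It then gives study size in person-time: "Assuming a 5% drop out rate, we anticipate" about "5,643 person months" (about 470 person-years) per arm.

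Protocol, Research Design and Methods, also speaks of a one-year study period, and allocates 6 clinics to peer educators without phones, 4 to peer educators with phones and 5 to control. Under Study Outcomes, morbidity and mortality are secondary.

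**The concern.** A comparison of simple risks is fair when everyone is at risk for the same length of time, or when the mix of longer and shorter follow-up is alike across arms. The Sample Size section suggests the first does not hold. The second is not assured, because clinics and not patients were randomised and there are only 15. How many of a clinic's patients were already in the pilot is a feature of that clinic, and so few units may not balance it.

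If one arm holds more patients with 18 months of observation, it will show more deaths, OIs and toxicities at the same underlying rate. A robust variance deals with correlation within clinics; it does not remove this shift in the estimate. An ANOVA on toxicity counts is affected in the same way, since expected counts grow with time observed. At stake is the interpretation of the secondary morbidity and mortality results.

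**Working it through.** **1. The plan's person-time figure.** Inputs from Protocol, Sample Size: 330 patients per arm, 18 months, 5% drop-out.

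330 × 18 × (1 − 0.05) = 5,643 person-months; 5,643 / 12 = 470 person-years.

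This matches the stated figure exactly, but only by giving every patient 18 months.

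**2. The same figure from the plan's own split.** With 800 of 1000 patients having 6 pilot months plus 12, and 200 having 12:

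(800 × 18 + 200 × 12) × 0.95 / 3 = 5,320 person-months per arm, or 443 person-years. That is 5.7% below 5,643. Mean planned follow-up is 0.8 × 18 + 0.2 × 12 = 16.8 months. So the sizing, too, passes over the unequal follow-up.

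**3. Effect on a risk ratio when the true rates are equal.** The Protocol gives no event rates for these outcomes and no pilot share by arm, so both are assumed here. Let *r* be a constant rate per person-year and *a* the share of an arm with 18 months:

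risk = 1 − [*a* exp(−1.5*r*) + (1 − *a*) exp(−*r*)].

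For *r* = 0.03, the 12-month risk is 2.96% and the 18-month risk 4.40%.

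| Share with 18 months, two arms | Mean follow-up (months) | Risks | Risk ratio |
|---|---|---|---|
| 80% v 80% | 16.8 v 16.8 | equal | 1.00 |
| 85% v 75% | 17.1 v 16.5 | 4.18% v 4.04% | 1.04 |
| 90% v 70% | 17.4 v 16.2 | 4.26% v 3.97% | 1.07 |
| 95% v 65% | 17.7 v 15.9 | 4.33% v 3.89% | 1.11 |

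For *r* = 0.06 and 90% v 70%, the risks are 8.33% v 7.77%, ratio again 1.07. Over a wider assumed range of 0.05 to 0.40 per person-year, 70% v 90% (the imbalance reversed) gives 0.93 to 0.95. The extreme of 60% v 100% gives 0.87 to 0.89.

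**4. Effect on mean toxicity counts.** Under a constant rate the ratio of means equals the ratio of mean follow-up: 17.4 / 16.2 = 1.07 for 90% v 70%.

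**5. Size against sampling error.** With 443 person-years per arm, rates of 0.03 and 0.06 give about 13 and 27 events per arm. The standard error of the log ratio is about √(2/13.3) = 0.39 and √(2/26.6) = 0.27, before any allowance for clustering. A spurious log ratio of 0.07 is therefore about 0.18 to 0.25 of a standard error.

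**The case against.** **The follow-up range is inferred.** The Protocol nowhere states 12 to 18 months, and it also describes a one-year study period. If events were counted only over that common year, patients enrolled by spring 2007 would have nearly equal follow-up and log-binomial regression would be reasonable. This stands as a caution. However, the Sample Size section builds its person-time on 18 months, and nothing says which window applies to these outcomes.

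**Adjustment might absorb it.** Pilot versus new enrolment could enter the model as a suspected confounder, or by the p < 0.15 rule. It could, but it is not named, so this is available and not assured.

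**The magnitude is built on assumptions.** This also stands. Event rates, constancy of the rate and arm mixes are all assumed. If event rates fall with time on treatment, 12- and 18-month risks differ less and the bias shrinks.

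**A stronger reading about retention is not supported.** A reader might infer that peer educators improve retention, that their patients are therefore seen longer and show more events, and that patients lost early are counted as event-free. The Protocol does not say how lost patients are handled. It assumes only 5% drop-out, which leaves little room for this mechanism, and nothing in the documents quantifies it. For deaths it is weaker still: Data Collection describes verbal autopsy with relatives and friends, so ascertainment need not end when a patient leaves the clinic. Verbal autopsy does not, however, equalise observation windows, and it does nothing for OIs or toxicity.

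**Conclusion.** The concern holds as a minor one. As written, the plan analyses mortality, OIs and toxicity without regard to time observed, while its own Sample Size section implies unequal observation. This goes beyond detail that a statistical analysis plan would normally supply, because the Protocol itself names the models.

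The distortion is about 1.07 on a true ratio of 1.00 for a 90% v 70% mix, within 1.04 to 1.11 for the three unequal mixes tabulated, and nil if mixes are balanced. It rests on assumed constant rates, assumed mixes and the inferred follow-up range, and it is well within sampling error at the assumed rates of 3 to 6 per 100 person-years.

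Three broader conclusions might be drawn but are not supported:

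- The primary outcomes are not at issue. Virologic failure at a fixed visit suits log-binomial regression, although the same sentence of the plan covers it.
- The study is not sized purely in person-time. The Sample Size section uses person-months, but the detectable effect is expressed in percentages of virologic failure (28% to 19.6%).
- Analysis of raw counts applies to drug toxicity only, which is listed both as binary and as a count. Mortality and OIs are listed as binary.

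**What to change.** Analyse first OI, first toxicity and mortality as rates on each patient's own person-time:

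- **Start:** the later of the patient's own entry to observation and one common calendar date applied to all arms, control included. A clinic's intervention start would not serve. Control clinics have no such date, and later entrants would be credited with event-free time before they were observed.
- **End:** event, last contact or study end. For mortality, continue to the last date on which vital status is known, so that deaths found by verbal autopsy after loss to the clinic are kept.
- **Model:** Poisson or negative binomial regression with a log person-time offset, or Cox regression for death, with the same clinic-level variance as the primary analysis. Use the offset count model in place of ANOVA for the number of toxicity events.

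Alternatively, restrict these outcomes to one fixed window common to all patients. Keep log-binomial regression for virologic failure at a fixed visit.

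The cost is some wording and a little more analysis. The dates needed should be obtainable from the routine clinical records and scheduled visits, though the Protocol does not list them explicitly. The rate analysis also assumes that loss to follow-up is non-informative for OIs and toxicity, and this should be stated.

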In the second project year we will scale up the peer educators and mobile phone technology to assess whether these interventions are sustainable, effective and appropriately cost effective. Qualitative studies will assess provider and patient attitudes towards these interventions.

Methods:

Study Design and Rationale

Research Design and Methods

Overview: A pilot peer educator/mobile phone intervention suggest that these programs are realistic in this resource-limited setting. However, there has been insufficient time and funding to assess the impact of these services on patient adherence and virologic outcomes. This proposal aims to build upon these early studies by:

- Extending the cluster-randomized peer educator and mobile phone programs for a one year study period in order to better assess impact on virologic treatment failure and adherence. Secondary outcomes include CD4 count changes, mortality, and morbidity...
- 2) If a positive impact is demonstrated during the first project year, we will scale-up the peer educator and mobile phone interventions to all communities in order to evaluate the effects on compliance and virologic outcomes after introduction of services, compared to the prior time period. These interventions will be further evaluated by an analysis of cost and sustainability.

Three Arm Cluster-Randomized Operations Research Study:

Study Design and Population: The program will continue with the current three armed randomization scheme of 6 clinics with peer educators but no mobile phones (Arm A), 4 clinics with peer educators and mobile phones (Arm B), and 5 clinics with no peer

educators. We will maintain a ratio of 15-20 patients per peer educator. New peer educators will be recruited and trained as necessary to maintain this patient ratio. Outcomes will be compared between clinic patients in the peer educator arms compared to the control arm, as well as between patients in clinics with peer educators equipped with mobile phones compared to clinics with peer educators without mobile phones, or the control condition. All analyses will use de-identified data. The study population will be ~1000 PEPFAR patients enrolled in the RHSP ART program by March, 2007. Process data will be collected on intervention implementation. Provider evaluations will be done via PEPFAR staff and peer educator surveys.

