Please note all patient records are routinely collected for clinical care so no additional consent is required and there is no risk to patients entailed by the evaluation, since deidentified data will be used.

Study Outcomes: The primary outcomes will be virologic failure (defined as viral load >400 copies/ml), and ARV adherence as measured by pill counts percentage (sum of ARV pills taken/sum of ARV pills prescribed). Secondary outcomes include change in CD4 count from baseline, morbidity (new opportunistic infection or drug toxicity), and mortality. These outcomes are recorded in clinical records and will be abstracted, and stripped of identifiers for analysis.

Data Collection: Patient Data: As part of the clinical service, viral loads are assessed every six months and CD4 counts every three months for one year, and then every six months thereafter through PEPFAR clinical monitoring and a parallel NIH funded R01 study to evaluate the ARV effects on HIV epidemiology and behaviors (1R01HD050180; PI [name]). Data on ARV adherence will be derived from peer educator home visit records and pill counts at the bi-weekly clinic visits as part of the routine clinical service. Morbidity outcomes and descriptive data (gender, age, WHO stage, Karnofsky score) will be collected through clinic records and questionnaires administered by ARV clinic staff to patients initiating ART, weekly for the first month, and then at 3, 6, 9, 12, and 24 months on ART. These are routinely collected data and do not add a research burden. Mortality data will be collected through verbal autopsy interviews with relatives and friends of deceased patients. This is routinely done as part of the Rakai cohort study. Mobile phone data will be captured in real-time with an automated, preprogrammed SMS system. This mobile phone intervention will use locally available phones and technology.

Additional operational evaluation procedures for Peer Educators:

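### Covariates for the virologic failure model are chosen by baseline difference at p < 0.15 or as unlisted suspected confounders; a short set should be named in advance

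*Protocol*

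**What the plan says.** Under Power Calculations or Statistical Plan, the Protocol uses log-binomial regression for dichotomous outcomes, including virologic failure, "adjusted for covariates found to differ between arms at p < 0.15 in univariate analyses, or suspected confounders". No covariate is named as always in the model, and the suspected confounders are not listed. Generalised estimating equations supply robust variances for clustering. That sentence follows the regression model and does not mention the screening tests.

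The same section plans descriptive analyses to "compare patients in each study arm at time of enrollment with respect to sociodemographic characteristics, WHO stage, viral load, CD4 count and Karnofsky score". This is the only place in the analysis text where baseline viral load appears. Study Outcomes makes viral load the basis of a primary outcome: "virologic failure (defined as viral load >400 copies/ml".

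On design, the same section states "This is an unmatched community randomized study", and Study Design and Population gives "6 clinics with peer educators but no mobile phones (Arm A), 4 clinics with peer educators and mobile phones (Arm B), and 5 clinics" without peer educators, 15 clinics in all. Sample Size anticipates about "330 patients in each of the three study arms".

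**The concern.** A covariate is worth adjusting for when it predicts the outcome. A test of baseline difference between randomised arms does not address that. It asks how far this allocation happened to fall out of balance, and a small p-value is mostly a chance event. A rule built on it can admit factors unrelated to outcome and pass over strong predictors that happen to be balanced.

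Viral load at enrollment is the clearest case. It is an earlier value of the outcome measure and is likely to be among the strongest predictors, yet the plan does not secure its place in the model.

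At stake is the adjusted relative risk for a primary outcome. Two analysts following the text faithfully could fit different models and report different estimates. With only 4 to 6 clinics per arm, precision matters, and covariates that predict nothing burden a robust variance that rests on 15 clusters.

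**Working it through.** The Protocol derives no figure here; 0.15 is a chosen threshold. The check is how the rule behaves when arms do not differ systematically.

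**Inputs.**
- Threshold 0.15, design effect 1.26 and between-cluster coefficient of variation k = 0.24 (Power Calculations or Statistical Plan).
- Failure proportion 28% and about 330 patients per arm (Sample Size).
- Clinics split 6/4/5 (Study Design and Population). Taking 5 clinics per arm gives 330/5 = 66 patients per clinic.
- Number of factors: five groups are named in the baseline comparison. Data Collection lists "descriptive data (gender, age, WHO stage, Karnofsky score"; adding viral load and CD4 count gives six. Independence between them is assumed.

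**1. Screening test of correct size.** Each unrelated factor enters with probability 0.15. P(at least one of m) = 1 − 0.85^m:
- m = 5: 1 − 0.444 = 0.556
- m = 6: 1 − 0.377 = 0.623

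The expected number of chance entries among six is 6 × 0.15 = 0.9.

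**2. Patient-level test that ignores clustering (an assumption).** For two arms, P(p < 0.15) = 2 × [1 − Φ(1.44/√DE)], where DE is the design effect.
- Stated DE of 1.26: 1.44/1.122 = 1.28, giving 0.20.
- Intracluster correlation from k: 0.24² × 0.28/0.72 = 0.0224. DE = 1 + 65 × 0.0224 = 2.46; 1.44/1.567 = 0.92, giving 0.36.

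For a three-arm test (chi-square, 2 df) the rate is 0.15^(1/DE): 0.22 at DE 1.26 and 0.46 at DE 2.46. A simulation with 6/4/5 clinics, about 330 patients per arm and 4,000 runs gave 22% and 47%. A test on clinic means in the same simulation held its size, at 14% to 15%.

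**3. How often viral load misses entry by the p-value route alone.** This is one minus the rates above: 85% with a correctly sized test, down to 54% with the three-arm test that ignores clustering at DE 2.46.

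**4. Possible bias from an imbalance that escapes.** With 330 v 330 and no clustering, the largest difference that stays above p = 0.15 is:
- 1.44 × √(2/330) = 0.11 SD for a continuous factor;
- 1.44 × √(2 × 0.28 × 0.72/330) = 5.0 percentage points for a binary factor at 28%.

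Suppose baseline failure multiplies the later failure risk by r (an assumption). With no treatment effect, an imbalance of 28% v 23.0% gives a relative risk of (0.230r + 0.770)/(0.28r + 0.72):

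| r | Spurious relative risk |
|---|---|
| 1.5 | 0.98 |
| 2 | 0.96 |
| 3 | 0.94 |

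**5. Precision.** The gain from including baseline viral load depends on how strongly it predicts later failure. The Protocol gives no such figure, so the loss is not quantified.

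**The case against.** The strongest defence is the word joining the two routes. A suspected confounder may enter at any p-value, and an analyst could well treat viral load as one. A reader might infer that viral load is dropped whenever its p-value is, say, 0.2; the text does not say that. Nor does it say when confounders are identified, so calling this route post hoc would be inference, and a list could stand in an analysis plan that is not shown. What remains is that the Protocol itself fixes the p < 0.15 rule and guarantees entry to no covariate.

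A reader might also infer that screening ignores clustering and so flags factors far more often than 15%. The Protocol is silent, and a clinic-level test keeps its size. The 36% figure further needs an intracluster correlation derived from the failure outcome to apply to age, sex, WHO stage and the rest. A claim that about three covariates would enter by chance would need eight variables at that rate; the Protocol does not give eight.

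Chance is not the only possible source of imbalance. The trial continues an existing allocation, with about 6 months of follow-up on about 800 pilot patients and ongoing recruitment, so patients may join clinics after allocation. That is a reason to adjust, but a better one for adjusting for known predictors than for whatever passes a test.

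Finally, the plan does examine outcomes by strata of covariates. It does not make that the criterion for selection.

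**Conclusion.** The point holds as a moderate weakness that should be corrected. The Protocol fixes a selection rule for a primary-outcome model that, with randomised clinics, responds mainly to chance imbalance instead of prognosis. The firm figures are 15% per unrelated factor and 56% to 62% for at least one of five or six; they assume a correctly sized test, independent factors and no systematic difference between arms. The rates of 20% and 36% are conditional on patient-level screening without allowance for clustering.

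Bias from one missed imbalance is likely to be a few percent of the relative risk (0.94 to 0.98 in the illustration), so the documents do not support reading the rule as a serious threat to validity. The main costs are unquantified loss of precision and an adjustment set that can change with the data.

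**What to change.** Delete the p < 0.15 clause and the open reference to suspected confounders. Name a short covariate set, used whatever the observed balance, in the log-binomial model with generalised estimating equations already planned; no change of method is needed. A reasonable set is viral load at enrollment, CD4 count and WHO stage, with age and sex if the model supports them.

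Viral load needs two definitions. Take it as the last value before exposure to the intervention, including the pilot, so that adjustment does not remove part of the effect. Enter it in a form that still varies in patients measured before starting ART; a split at 400 copies/ml would barely vary in them.

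Report the unadjusted estimate beside the adjusted one, and keep the baseline comparison descriptive.

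The Protocol already lists these variables among its routine data or baseline comparisons, so the cost is almost entirely wording. There is a small downside: some patients may lack a viral load from before the intervention, and with 15 clinics the set must stay short.

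### With 9 to 11 clinics per pairwise contrast, ordinary GEE robust variances give the virologic-failure tests a type I error of about 11 to 13%, not the stated 5%

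*Protocol*

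**What the plan says.** The section on the three-arm cluster-randomized study allocates "6 clinics with peer educators but no mobile phones (Arm A), 4 clinics with peer educators and mobile phones (Arm B), and 5 clinics" to control, 15 in all. It plans each pairwise contrast: "Outcomes will be compared between clinic patients in the peer educator arms compared to the control arm", and phones against no phones or control. The power section also considers the two peer-educator arms together against control.

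Virologic failure is one of two primary outcomes. Under Power Calculations or Statistical Plan it is analysed by log-binomial regression, adjusted for covariates that differ between arms or are suspected confounders. Clustering is handled in one sentence: "Adjustment for clustered data will use general estimating equations (GGE) to estimate robust variances". The error rate appears in the power statement of the same section: "With a two-sided α = 0.05 and 1-β of 0.80". That section calls the design effects modest. It does not discuss the small number of clinics.

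**The concern.** The sandwich variance is justified by a large number of clusters, not of patients. With 4 to 6 clinics per arm two things go wrong. The residuals are measured around arm means fitted to those same few clinics, so the variance is too small on average. It is also estimated with few degrees of freedom, so a normal reference is too narrow. Both push the test towards rejection and make confidence intervals too short.

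The stake is practical. The overview of the research design makes scale-up to all communities depend on a positive first-year result. The contrast with the fewest clinics, phones against control, is the worst affected.

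**Working it through.** **Inputs from the protocol.** Clinics: A = 6, B = 4, control C = 5. Patients: "330 patients in each of the three study arms", so about 55, 82.5 and 66 per clinic. Failure p = 0.28. Clustering: "a coefficient of variation (k) between clusters of 0.24". Target level: two-sided 0.05.

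**Inputs assumed.** Uncorrected sandwich, cut-off 1.96, equal clinic sizes within arm. Varying clinic sizes are tried separately.

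**Hand check.** For an arm of J clinics with n patients each, the variance of the log risk is about V = [k² + (1−p)/(pn)]/J, with k² = 0.0576 and (1−p)/p = 2.571.

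- A: (0.0576 + 2.571/55)/6 = 0.01739
- B: (0.0576 + 2.571/82.5)/4 = 0.02219
- C: (0.0576 + 2.571/66)/5 = 0.01931

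The sandwich estimates V(J−1)/J on average: 0.01449, 0.01664 and 0.01545. The ratio of estimated to true variance for each contrast is:

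- A v C: 0.02994/0.03670 = 0.816
- B v C: 0.03209/0.04150 = 0.773
- B v A: 0.03113/0.03958 = 0.787

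A cut-off of 1.96 then acts like 1.96 × √ratio on a t scale with clusters minus 2 df:

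- A v C: 1.770 on 9 df, two-sided tail 11.0%
- B v C: 1.724 on 7 df, 12.8%
- B v A: 1.738 on 8 df, 12.0%

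**Simulation under the null.** Beta-binomial clinics, about 330 patients per arm, 40,000 trials per setting (Monte Carlo standard error about 0.16 points). Repeat runs agree within about 0.3 points.

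| Contrast (clinics) | Sandwich, z, equal sizes | Sandwich, z, size CV 0.4 (assumed) | Clinic-level t test, equal sizes |
|---|---|---|---|
| A v C (11) | 11.1% | 12.4% | 5.0% |
| B v C (9) | 12.8% | 14.4% | 4.8% |
| B v A (10) | 12.1% | 13.6% | 4.6% |
| A+B v C (15) | 10.4% | 12.0% | 5.0% |

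The clinic-level t test stays at 4.5 to 5.2% when sizes vary as well.

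**What does not cure it.**

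- *Little clustering.* At k = 0 the pairwise rates are still 11.0 to 12.6%. The cause is the number of clinics.
- *One model for all 15 clinics.* A three-arm log-binomial GEE with exchangeable correlation gives 10.6%, 10.9% and 13.3% (1,000 trials, standard error about 1 point).
- *A t reference alone.* The pairwise rates are still 7.0 to 7.5% with equal sizes.

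**What does.** Multiplying each arm's variance by J/(J−1) and using t on clusters minus 2 df gives 4.9%, 4.9% and 5.1% for the pairwise contrasts with equal sizes. The pooled contrast stays at 5.9%. At a size CV of 0.4 the range is 5.8 to 6.9%.

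**The case against.** The strongest reply is that the sentence names GEE and robust variances and nothing more. It does not state an uncorrected sandwich or a 1.96 cut-off, and a bias-corrected sandwich would fit the same words. The type of correction and the reference distribution are often left to a statistical analysis plan, which is not at hand here. This part stands: the rates are conditional on the plain reading, and the protocol does not rule out a correction. It does not remove the point. The protocol has already chosen the method for a primary outcome, and the ordinary form of that method does not deliver the stated level with this number of clinics.

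Three stronger readings are tempting and not supported.

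- A reader might take 15% as the error rate. That end of the range needs unequal clinic sizes, and the protocol gives no clinic sizes.
- A reader might conclude that the protocol ignores clustering. It does not; it adjusts for it with a method unsuited to few clusters.
- A reader might extend the figures to adherence, the other primary outcome. The protocol assigns that to tests and analysis of variance, which were not examined here.

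Covariate adjustment probably adds some inflation, since small checks with null covariates gave increases of 0 to 3 points. These are too imprecise to quote as a size.

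**Conclusion.** The point holds in conditional form. If the planned GEE analysis is run with the ordinary sandwich and a normal reference, the nominal 5% tests of virologic failure have a true size of about 11 to 13% pairwise and 10 to 11% pooled. Nominal 95% intervals for the pairwise contrasts then cover about 87 to 89%.

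This rests on 28% failure, k = 0.24, about 330 patients per arm and equal clinic sizes within arm. The value of k hardly matters. Unequal sizes make it worse: about 12 to 15% at an assumed CV of 0.4. The error is at least double the nominal level in every setting tried, so the text should be changed before the analysis.

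**What to change.** Make the primary test of virologic failure a two-stage clinic-level analysis. First fit a patient-level model with the covariates but without arm, and form observed over expected failures for each clinic. Then compare the clinics between arms by a t or permutation test.

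The alternative is to keep GEE and name a bias-corrected sandwich (Kauermann-Carroll or Fay-Graubard) with a t reference on clusters minus 2 df. A simple J/(J−1) correction still leaves about 6 to 7% when clinic sizes vary, so the clinic-level analysis is the safer choice.

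No design or data change is needed, but the cost is more than wording. With the J/(J−1) correction and a t reference, intervals widen by these factors over the uncorrected ones:

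- A v C: 2.262/1.770 = 1.28
- B v A: 2.306/1.738 = 1.33
- B v C: 2.365/1.724 = 1.37

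The stated 80% power for a rate ratio of 0.70 must therefore be recomputed under the corrected test and restated.

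### CD4 change is to be analysed by tests/ANOVA with no covariate although baseline CD4 is collected; adjusting for it would gain precision and protect against chance imbalance between a few clinics

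*Protocol*

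**What the plan says.** In the Protocol, Power Calculations or Statistical Plan, the dichotomous outcomes go to log-binomial regression. Those models adjust for covariates that differ between arms at p < 0.15 or are thought to confound. Generalised estimating equations follow for the clustering. The next sentence reads: "For continuous data (e.g., adherence percent, CD4 changes from baseline to follow-up, number of drug toxicity events) we will use tests and analysis of variance". It names no covariate.

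Baseline CD4 is available. The same section states: "Descriptive analyses will compare patients in each study arm at time of enrollment with respect to sociodemographic characteristics, WHO stage, viral load, CD4 count". The Data Collection section adds that "viral loads are assessed every six months and CD4 counts every three months for one year, and then every six months thereafter". CD4 change from baseline is a named secondary outcome.

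Adherence differs in two ways. It is not among the variables compared at enrollment, and the log-binomial sentence also mentions it, so some relative-risk form of adherence is adjusted. The percentage form goes to tests/ANOVA.

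**The concern.** The plan tabulates baseline CD4 by arm but gives the CD4 analysis no means of using it other than subtraction. Subtraction assumes that a patient who starts one unit lower also ends one unit lower. If the true slope is below 1, an arm that starts low by chance tends to show a larger rise (regression to the mean), and the change score credits that rise to the intervention. With only 6, 4 and 5 clinics in Arm A, Arm B and control, a chance difference in mean baseline is plausible and precision is scarce. This is separate from clustering: a correctly clustered test of raw change would still be unadjusted.

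**Working it through.** **Plan's own figure.** There is none for CD4. The statement "With a two-sided α = 0.05 and 1-β of 0.80" concerns virologic failure only. No SD, effect size, correlation or power is given for any continuous outcome. I therefore assume 80% power for the unadjusted CD4 analysis as a benchmark, and vary the correlation rho between baseline and follow-up CD4.

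**Inputs.** From the protocol: 6, 4 and 5 clinics; about 1000 patients, so 1000/15 ≈ 67 per clinic; k = 0.24; 28% failure; design effect about 1.26. Assumed: rho from 0.3 to 0.9; equal SD at baseline and follow-up; rho the same within and between clinics, unless stated.

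**Step 1: variance ratio.** With patient SD s:
- Change score: 2s²(1 − rho).
- Baseline-adjusted: s²(1 − rho²).
- Ratio: (1 − rho²) / [2(1 − rho)] = (1 + rho)/2 = 0.65, 0.75, 0.85, 0.95 at rho 0.3, 0.5, 0.7, 0.9.

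**Step 2: power.** Clinic-level t test, two-sided 0.05, df = clinics − 2. The noncentrality that gives 80% unadjusted is 3.15 for A v control (df 9). Divide it by the square root of the ratio:

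| rho | A v control, df 9 | Same, one df lost | B v control, one df lost (df 6) |
|---|---|---|---|
| 0.3 | 93.4% | 92.6% | 91.9% |
| 0.5 | 89.8% | 88.8% | 87.9% |
| 0.7 | 85.9% | 84.8% | 83.8% |
| 0.9 | 82.0% | 80.7% | 79.7% |

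The normal approximation, Phi(2.80/√ratio − 1.96), agrees: 93.5, 89.9, 86.0 and 82.0%. From a 60% starting point, rho 0.5 gives 72%.

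**Step 3: if adjustment shrinks only within-clinic variance (rho 0.5).** Ratio = [0.75(1 − ICC)/67 + ICC] / [(1 − ICC)/67 + ICC]. The protocol's k implies ICC = 0.24² × 0.28/0.72 = 0.0224 for virologic failure; I borrow it for CD4.
- ICC 0.01: ratio 0.851, power 85.9%.
- ICC 0.0224: ratio 0.901, power 83.9%.
- ICC 0.05: ratio 0.945, power 82.2%.

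With the protocol's design effect instead, the ratio is (0.75 + 0.26)/1.26 = 0.802 and power is 87.9% (normal approximation).

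**Step 4: chance imbalance.** SD of the A v control difference in mean baseline = √[(1 + 66 × 0.0224)/67 × (1/6 + 1/5)] = 0.116 patient-SDs. A share (1 − rho) of any imbalance passes into the change contrast with reversed sign. At rho 0.5, an imbalance of 1.5 of its SDs (0.175) moves the contrast by 0.087 patient-SDs.

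**Step 5: error rates.** 200,000 simulated null trials, 6 v 5 clinics, rho 0.5. Over all trials, both the change score and the adjusted test reject in about 5%. Among the roughly 13% of trials with imbalance beyond 1.5 SDs, the change score rejects in just under 12%. The adjusted test rejects in about 5%, whether the slope is known or estimated from the 11 clinics (8 df).

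**The case against.** **Shorthand, not a decision.** The sentence on continuous data does not say unadjusted, and covariate lists are commonly left to the SAP. That has some force. But the plan names a change score and ANOVA for CD4, and places adjustment in the sentence on a different class of outcome. The later mention of stratified analyses and interaction terms does not supply a baseline adjustment. The point proposes a better method than the one stated; it is more than a request for detail.

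**A reader might infer that the change score is biased or inflates type I error.** It does not. Under randomisation, a correctly clustered change-score test is unbiased and holds 5% overall. The 12% applies only given a large observed imbalance.

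**A reader might extend the point to the adherence outcome.** The documents do not support that. No baseline adherence is described, and a pill count cannot precede ART. The six months of data on about 800 patients come from the pilot, whose three-arm allocation is continued, so those counts may already reflect the intervention. Adjusting for them could remove effect. Routine "pill counts at the bi-weekly clinic visits as part of the routine clinical service" may give some patients an earlier value, since ART delivery began in June 2004. The number is unknown because no randomisation date is stated.

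**A reader might want a single figure for lost power.** None can be derived from the protocol; the range depends on rho and on the assumed 80%.

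**Conclusion.** The point holds for CD4 change, a secondary outcome. The protocol specifies an analysis without covariates when the natural covariate is already collected. Assuming 80% unadjusted power and equal correlation within and between clinics, adjustment gains about 13 points at rho 0.3, 10 at 0.5, 6 at 0.7 and 2 at 0.9. At rho 0.5 the gain falls to about 2 to 6 points if only within-clinic variance shrinks, at ICCs from 0.05 down to 0.01. At rho 0.9, losing a degree of freedom can cancel it. What is gained is precision and protection against chance baseline imbalance; overall type I error is not at issue. For adherence percent, all that can be said is that no covariate is named for it; no power gain is claimed.

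**What to change.** For CD4, replace the sentence on continuous data with wording such as: follow-up CD4 (or CD4 change) will be compared between arms in a linear model that accounts for clustering by clinic and adjusts for the patient's own CD4 before exposure to the intervention, meaning the last value before the clinic's randomisation, or the value at ART start if later. Keep the unadjusted change as a descriptive summary.

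For adherence percent, adjust for a prior pill count only where a clinic-measured count from before the clinic's randomisation exists.

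The cost is a sentence or two. CD4 needs no new measurement, but each clinic's randomisation date must be recorded so that the baseline can be identified. A clinic-level version of the adjustment uses up to one degree of freedom.
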